### Reporting Information for SAEs

A report ***must be submitted*** to Biogen regardless of the following:

- Whether or not the participant has undergone study-related procedures
- Whether or not the participant has received study treatment
- The severity of the event
- The relationship of the event to study treatment

To report initial or FU information on an SAE, fax or email a completed SAE form; refer to the Study Reference Guide for complete contact information.

#### 15.3.3.1. Deaths

Death is an outcome of an event. The event that resulted in death should be recorded on the appropriate CRF. All causes of death must be reported as SAEs within 24 hours of the site becoming aware of the event. The Investigator should make every effort to obtain and send death certificates and autopsy reports to Biogen. The term death should be reported as an SAE only if the cause of death is not known and cannot be determined.

#### 15.3.4. Suspected Unexpected Serious Adverse Reactions

SUSARs are SAEs that are unexpected and judged by the Investigator or Biogen to be related to the study treatment administered.

Appropriate personnel at Biogen will unblind SUSARs for the purpose of regulatory reporting. Biogen will submit SUSARs (in blinded or unblinded fashion) to regulatory agencies according to local law. Biogen will submit SUSARs to Investigators in a blinded fashion.

### 15.4. Procedures for Handling Special Situations

#### 15.4.1. Pregnancy

**Participants should not become pregnant during the study and for 5 months after their last dose of study treatment.** If a female participant becomes pregnant, study treatment must be discontinued *immediately*.

The Investigator must report a pregnancy occurring in a female participant by faxing or emailing the appropriate form to Biogen within 24 hours of the study site staff becoming aware of the pregnancy; refer to the Study Reference Guide for complete contact information. The Investigator or study site staff must report the outcome of the pregnancy to Biogen. A pregnancy is not considered an AE and should not be recorded on the AE CRF.

Congenital abnormalities and birth defects in the offspring of male or female participants should be reported as an SAE if conception occurred during the study treatment period.

CONFIDENTIAL

The information contained herein may not be used, disclosed, or published without the written consent of  
Biogen MA Inc.

### **15.4.2. Overdose**

An overdose is any dose of study treatment administered to a participant or taken by a participant that exceeds the dose assigned to the participant according to the protocol. Overdoses are not considered AEs and should not be recorded as an AE on the CRF; however, all overdoses must be recorded on an Overdose form and faxed or emailed to Biogen within 24 hours of the site becoming aware of the overdose. An overdose must be reported to Biogen even if the overdose does not result in an AE. If an overdose results in an AE, the AE must be recorded. If an overdose results in an SAE, both the SAE and Overdose forms must be completed and faxed or emailed to Biogen; refer to the Study Reference Guide for complete contact information. All study treatment-related dosing information must be recorded on the dosing CRF.

### **15.4.3. Medical Emergency**

In a medical emergency requiring immediate attention, study site staff will apply appropriate medical intervention, according to current standards of care. The Investigator (or designee) should contact the study's Medical Director. Refer to the Study Reference Guide's Official Study Contact List for complete contact information.

#### **15.4.3.1. Unblinding for Medical Emergency**

In a medical emergency when knowledge of the participant's treatment assignment may influence the participant's clinical care, the Investigator and, if applicable, designated personnel at Biogen may access the participant's treatment assignment by IRT. The Investigator must document the reasons for unblinding in the participant's source documents. The Investigator is strongly advised not to divulge the participant's treatment assignment to any individual not directly involved in managing the medical emergency, nor to personnel involved with the analysis and conduct of the study. The Investigator can contact Biogen or designee to discuss such situations.

## **15.5. Contraception Requirements**

All women of childbearing potential must ensure that effective contraception is used during the study and for 5 months after their last dose of study treatment. In addition, female participants should not donate eggs for the duration of the study and for at least 5 months after their last dose of study treatment.

For the purposes of this study, women who do not meet one of the following criteria are considered to be physiologically capable of becoming pregnant and are, therefore, defined as women of childbearing potential:

- Postmenopausal
  - 12 continuous months of natural (spontaneous) amenorrhea without an alternative medical cause and a serum FSH level > 40 mIU/mL
  - 6 weeks after surgical bilateral oophorectomy with or without hysterectomy
- Posthysterectomy
- Female surgical sterilization (e.g., bilateral tubal ligation)

CONFIDENTIAL

The information contained herein may not be used, disclosed, or published without the written consent of Biogen MA Inc.

For the purposes of the study, effective contraception is defined as use of at least 1 of the following:

For females:

- Established use of oral, injected, implanted, intravaginal, or transdermal hormonal methods of contraception.
- Placement of an intrauterine device or intrauterine hormone-releasing system.
- Barrier methods of contraception with use of a spermicide: condom or occlusive cap (diaphragm or cervical/vault caps) with spermicidal foam/gel/film/cream suppository. The use of barrier contraceptives should always be supplemented with the use of a spermicide.
- Sex with a male who has undergone surgical sterilization (with the appropriate postvasectomy documentation of the absence of sperm in the ejaculate).

True abstinence, when this is consistent with the preferred and usual lifestyle of the participant, can be considered an acceptable method of contraception based on the evaluation of the Investigator who should also take into consideration the duration of the clinical trial. Periodic abstinence (e.g., calendar, ovulation, symptothermal, postovulation methods) and withdrawal are not considered acceptable methods of contraception.

Pregnancy reporting is described in Section [15.4.1](#).

## **15.6. Safety Responsibilities**

### **15.6.1. The Investigator**

The Investigator's responsibilities include the following:

- Monitor and record all AEs, including SAEs, regardless of the severity or relationship to study treatment.
- Determine the seriousness, relationship, and severity of each event.
- Determine the onset and resolution dates of each event.
- Monitor and record all pregnancies, and follow up on the outcome of the pregnancy in female participants.
- Complete an SAE form for each SAE and fax or email it to Biogen within 24 hours of the study site staff becoming aware of the event.
- Pursue SAE FU information actively and persistently. FU information must be reported to Biogen within 24 hours of the study site staff becoming aware of new information.
- Ensure all AE and SAE reports are supported by documentation in the participants' medical records.
- Pursue AE FU information, if possible, until the event has resolved or become stable.

CONFIDENTIAL

The information contained herein may not be used, disclosed, or published without the written consent of Biogen MA Inc.

- Report SAEs to local ethics committees, as required by local law.

### **15.6.2. Biogen**

Biogen's responsibilities include the following:

- Before study site activation and participant enrollment, the Clinical Monitor is responsible for reviewing with study site staff the definitions of AE and SAE, as well as the instructions for monitoring, recording, and reporting AEs and SAEs.
- Biogen is to notify all appropriate regulatory authorities, central ethics committees, and Investigators of SAEs, as required by local law, within required time frames.

CONFIDENTIAL

The information contained herein may not be used, disclosed, or published without the written consent of  
Biogen MA Inc.

## **16. STATISTICAL METHODS AND DETERMINATION OF SAMPLE SIZE**

The objectives of the study and the endpoints to be analyzed are listed in Section 6.

### **16.1. Part A (SAD) and Part B (MAD)**

The ITT population is defined as all randomized participants who receive at least 1 or a part of 1 dose of study treatment.

#### **16.1.1. Clinical Function**

##### **16.1.1.1. Analysis Population**

The clinical function set is defined as the subset of the ITT population who have at least 1 postdose measurement.

All participants receiving placebo will be combined to form placebo control groups for Part A (SAD) and for Part B (MAD). A separate statistical analysis will be performed for Part A (SAD) and for Part B (MAD).

##### **16.1.1.2. Methods of Analysis**

The change and percent change from baseline in [REDACTED] HHD, ALSFRS-R, SVC, [REDACTED] will be summarized by visit and dose level using descriptive statistics and, where warranted, presented graphically. A 2-sample Student's t-test will be used to compare these data between each dose of BIIB067 and placebo at a 2-sided alpha level of 0.10.

#### **16.1.2. Pharmacokinetics**

##### **16.1.2.1. Analysis Population**

The PK population is defined as the subset of the ITT population of participants with at least 1 postdose PK measurement.

##### **16.1.2.2. Methods of Analysis**

Plasma and CSF PK parameters and BIIB067 concentrations in plasma and CSF for the PK population will be summarized using descriptive statistics and, where warranted, presented graphically.

#### **16.1.3. Pharmacodynamics**

##### **16.1.3.1. Analysis Population**

The PD population is defined as the ITT population of participants with at least 1 PD measurement after baseline.

CONFIDENTIAL

The information contained herein may not be used, disclosed, or published without the written consent of Biogen MA Inc.

### **16.1.3.2. Methods of Analysis**

Changes and percent changes from baseline for total SOD1 protein levels will be summarized and presented by visit and by dose level. A 2-sample Student's t-test will be used to compare each dose of BIIB067 and placebo at a 2-sided alpha level of 0.10.

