##### 6.1.2.1. Secondary Endpoint

The secondary endpoint is the change from baseline in CSF levels of total SOD1 protein.

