### **16.1.8. Sample Size Considerations**

The maximum sample size of 36 participants for Part A of the study (SAD) is based on clinical rather than statistical considerations. Participants will be randomized to receive BIIB067 or placebo in a 3:1 ratio in each cohort. Each cohort will have a minimum of 4 participants (3 active and 1 placebo), and a maximum of 12 participants (9 active and 3 placebo). The final number for each cohort will be dependent on the DLT profile. If no DLT occurs in any dose level, then a total of 20 participants (15 active and 5 placebo) will be randomized. This design will allow for adequate evaluation of the safety of BIIB067, should DLT be encountered, as well as minimize participant exposure at subtherapeutic single doses.

For Part B (MAD), up to 48 participants will be enrolled in up to 4 cohorts, with up to 9 participants randomized to receive BIIB067 and 3 participants randomized to receive placebo for each cohort. This design will provide approximately 80% power to detect a difference in total SOD1 protein reduction between 25% from the BIIB067 group and 12% from the placebo group at a 10% significance level. The sample size calculation assumes the same 10.5% SD in the 2 treatment groups.

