#### **16.2.3.2. Methods of Analysis**

The PD endpoint, CSF total SOD1 protein at Day 197, will be the primary endpoint in the non-mITT population due to their likely slow clinical function decline. This is also the highest-ranked secondary endpoint in the sequential testing procedure for the mITT population, and NfL in plasma at Day 197 is the second highest ranked secondary endpoint. For other biomarkers, analyses will be performed for each of the mITT and non-mITT populations with nominal p-values presented. For each of the PD/biomarker endpoints, MI will be used to impute missing values. An ANCOVA model for log ratio to baseline will be performed on change from baseline values on the log scale for each of the imputed datasets for each PD/biomarker endpoint. The model will include covariates for the corresponding baseline value, i.e., log value, baseline disease duration since symptom onset, and use of riluzole or edaravone. Least square means (i.e., geometric mean ratios) for each treatment group with standard errors as well as treatment differences will be presented with 95% confidence intervals and p-values. The other exploratory PD/biomarker endpoints that will be analyzed in this way are NfL in CSF, and pNfH in CSF and plasma.

[REDACTED]. Treatment differences at other visits will also be presented with nominal p-values.

CONFIDENTIAL

The information contained herein may not be used, disclosed, or published without the written consent of Biogen MA Inc.

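### The Part A/B t-test for total SOD1 is valid and meets its stated power, but it ignores baseline and the other dose groups, and its tested scale is not named

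*Protocol*

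**What the plan says.** Protocol section 6.1.2.1 defines the endpoint for Parts A and B: "The secondary endpoint is the change from baseline in CSF levels of total SOD1 protein". Section 16.1.3.2 first sets out the descriptive part: "Changes and percent changes from baseline for total SOD1 protein levels will be summarized and presented by visit and by dose level". It then gives the test, of the two-sample Student form: "t-test will be used to compare each dose of BIIB067 and placebo at a 2-sided alpha level of 0.10". That sentence names neither a tested variable nor a covariate.

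Section 16.1.1.1 pools placebo participants within each part. Section 16.1.8 gives the Part B power basis: "approximately 80% power to detect a difference in total SOD1 protein reduction between 25% from the BIIB067 group and 12% from the placebo group". It sets alpha at 10% and takes an SD of 10.5% in both groups, with cohorts of 9 active and 3 placebo participants. Tables 1 and 2 schedule a predose CSF sample on Day 1 for every participant, so a baseline value is planned for all.

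For Part C, section 16.2.3.2 treats the same marker differently: "An ANCOVA model for log ratio to baseline will be performed on change from baseline values on the log scale", with log baseline, disease duration and riluzole or edaravone use as covariates.

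**The concern.** Three features of the planned Part A/B test can be improved.

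- **Baseline is not used.** In groups this small, chance differences in baseline SOD1 between a dose group and pooled placebo pass into the comparison to the extent that baseline predicts the outcome.
- **Each test stands alone.** A Part B comparison of 9 v 12 estimates its variance with 19 degrees of freedom, although 48 participants in five groups would supply 43. A Part A comparison of 3 v 5 has 6, although 20 participants would supply 15.
- **The tested scale is open.** Section 6.1.2.1 speaks of change, section 16.1.8 is powered on percent reduction, and section 16.1.3.2 mentions both before naming a test. Two scales can give two p-values for one endpoint.

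At stake is the precision of the dose-by-dose SOD1 estimates, not the validity of the test.

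**Working it through.** **Inputs.** Difference 25 − 12 = 13 points, SD 10.5, two-sided alpha 0.10, 9 active per Part B cohort (section 16.1.8). Pooled placebo in Part B is 3 × 4 = 12 with four cohorts, or 9 with three. Part A without dose-limiting toxicity has 3, 3, 3 and 6 active and 5 pooled placebo. The correlation r between baseline and the outcome is not in the protocol; 0 to 0.5 is assumed.

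**1. The stated power.** Power comes from the noncentral t distribution with noncentrality 13 / (10.5 × √(1/n1 + 1/n2)) and n1 + n2 − 2 degrees of freedom.

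- 9 v 9: noncentrality 2.626, 16 df, power 80.7%.
- 9 v 12: noncentrality 2.808, 19 df, power 85.6%.

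The stated figure of about 80% is reproduced at 9 v 9. With the four cohorts now planned it is conservative.

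**2. Pooling the variance, with no covariate.** The noncentrality stays the same and the degrees of freedom become participants minus groups.

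- Part B, 9 v 12: 48 − 5 = 43 df, power 86.8%, a gain of 86.8 − 85.6 = 1.2 points.
- Part A, 20 − 5 = 15 df: 3 v 5 (noncentrality 1.695) goes from 44.4% to 49.0%; 6 v 5 (noncentrality 2.045) goes from 59.6% to 62.0%.

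**3. One ANCOVA per part.** The statistic is (dy − b·dx) / √(s²(1/n1 + 1/n2 + dx²/Sxx)). Here dy and dx are the differences in mean outcome and mean baseline, b is the common within-group slope, Sxx is the within-group baseline sum of squares over all groups, and the degrees of freedom are participants minus groups minus 1 (42 in Part B, 14 in Part A). The dx² term carries the cost of chance baseline imbalance. Simulated with the same 13-point effect and total SD 10.5:

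| Comparison | Planned t-test | r = 0 | r = 0.3 | r = 0.5 |
|---|---|---|---|---|
| Part B, 9 v 12 | 85.6% | about 86% | about 89% | about 93% |
| Part A, 3 v 5 | 44.4% | about 47% | about 49% | about 56% |
| Part A, 6 v 5 | 59.6% | about 59% | about 63% | about 70% |

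At r = 0 the covariate returns part of the pooling gain. In Part A it repays itself only from about r = 0.3, where 49% and 63% compare with 49.0% and 62.0% from pooling alone.

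**4. A pairwise ANCOVA would not do.** Fitted to two groups at a time, simulated power at 9 v 12 is 83.8% at r = 0, 86.6% at r = 0.3 and 91.7% at r = 0.5. At 3 v 5 it is 38.5%, 40.8% and 46.4%. This loses against the t-test below about r = 0.25 in Part B and about 0.45 in Part A. The case therefore depends on one model across all groups of a part.

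These figures carry the protocol's percent-scale effect and SD into the model as a standardised effect. The protocol gives no log-scale SD for Part B.

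**The case against.** The strongest reply is that nothing is wrong with the planned test. It is valid, its power statement holds, and it serves a secondary endpoint in a dose-escalation stage. That stands, and it makes this an efficiency point.

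A reader might infer that section 16.1.3.2 orders separate t-tests on change and on percent change. It does not: both are summarised, and the test sentence names no variable. Section 16.1.8 points to percent change. Naming the scale is also detail that an analysis plan may supply, so the ambiguity alone would be a small matter.

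A reader might also infer that power is being given away. That is not shown. The gain depends on a correlation the protocol does not state, and part of it comes from pooling variance, not from the covariate. The common variance is also an assumption: section 16.1.8 makes it only for the two groups compared.

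Nor does the Part C model contradict the Part A/B test. Different stages may use different methods, and no formal comparison of Part B with Part C is planned.

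Two practical objections have weight. Section 5.3.2 already reports a statistically significant SOD1 reduction at 100 mg, and sections 5.5 and 16.2.7 use interim A/B data, so a change now follows sight of results. Section 7.1.1 also lets Part A participants from the two lower-dose cohorts re-enrol and be rerandomised, so one person can appear in two dose groups. The second difficulty affects the planned t-tests too, since a person can contribute twice to pooled placebo or to both sides of a comparison.

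**Conclusion.** The point holds as a recommended improvement, not as an error. The planned t-test is valid and meets its stated power, but it leaves aside information that one model per part would use at no data cost.

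The size is modest in Part B: from 85.6% to about 86-93% at 9 v 12, of which 1 to 2 points come from variance pooling alone. In Part A the range is 44% to about 47-56% at 3 v 5, and 60% to about 59-70% at 6 v 5, so with no baseline correlation the larger Part A cohort gains nothing.

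All of this rests on an assumed r of 0 to 0.5, a common variance across doses and independent observations. The documents do not support a claim that Part B is underpowered, that two scales are formally tested, or that Parts A/B and Part C are inconsistent.

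**What to change.** In section 16.1.3.2, name the log ratio to baseline as the single tested variable. Replace the separate t-tests with one ANCOVA per part, with dose group as a factor including pooled placebo and log baseline as covariate. Report geometric mean ratios of each dose to placebo with 90% confidence intervals, which match the two-sided 0.10 level. Keep change and percent change as descriptive summaries.

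The cost is one degree of freedom for the covariate and the common-variance assumption, which should be checked against the observed spread by dose. Because interim A/B results are known, the amendment should be dated as made after them and the planned t-test reported alongside. State how Part A participants who re-enrol are handled, as repeated observations on one person. No new data, visits or participants are needed.

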### **16.1.4. Biomarker and Pharmacogenomic Analyses**

#### **16.1.4.1. Analysis Population**

The biomarker population is defined as the ITT population of participants with at least 1 postbaseline biomarker measurement.

#### **16.1.4.2. Methods of Analysis**

CSF and blood samples may be assayed for biomarkers that may include, but will not be limited to, [REDACTED] pNfH, and NfL.

Exploratory potential biomarker candidates related to BIIB067 biological activity will be summarized using descriptive statistics and will be presented by dose level.

Summary statistics (raw and logarithmic scale) for the above potential biomarkers will be calculated and presented by dose level and by visit, and their mean and median levels will be plotted over time, as appropriate.

See Section 4 for information on when samples will be collected.

Sampling for this analysis will be approved at the discretion of each site's ethics committee. If a site's ethics committee does not approve the sampling for the analysis, this section will not be applicable to that site.

### **16.1.5. Safety**

#### **16.1.5.1. Analysis Population**

The safety population is defined as the ITT population of participants.

#### **16.1.5.2. Methods of Analysis**

##### **16.1.5.2.1. Adverse Events**

AEs will be coded using MedDRA.

The incidence of all AEs and SAEs will be summarized by system organ class and preferred term for each dose level. AEs will also be summarized by severity and relationship to study treatment. Narratives of deaths, SAEs, and AEs that led to study withdrawal, at a minimum, will also be provided.

##### **16.1.5.2.2. Clinical Laboratory Results**

Clinical laboratory evaluations include hematology, coagulation, blood chemistry, and urinalysis. Laboratory data will be summarized using shift tables. The number and percentage of participants with shifts from baseline to high or low status for hematology, coagulation, and

CONFIDENTIAL

The information contained herein may not be used, disclosed, or published without the written consent of  
Biogen MA Inc.

blood chemistry, and shifts from baseline to high or positive status for urinalysis will be presented by dose level. In addition, summaries of the shift from baseline to the maximum postbaseline value and the shift from baseline to the minimum postbaseline value will be presented by cohort.

